4.2 Exclusion Criteria

Subjects meeting any of the exclusion criteria at baseline will be excluded from study participation.

- 4.2.1 Allogeneic hematopoietic cell transplantation within 5 years of study drug administration
- 4.2.2 Is currently participating and receiving study therapy or has participated in a study of an investigational agent and received study therapy or used an investigational device within 4 weeks of the first dose of treatment.
- 4.2.3 GM-CSF or G-CSF use within 2 weeks of study treatment and throughout the study
- 4.2.4 Prior checkpoint inhibitor therapy including anti-PD1, anti-PD-L1, anti-CTLA4, anti-CD137, or anti-PD-L2 therapy
- 4.2.5 Prior treatment with any CD19-directed therapy (e.g. blinatumomab, CD19-directed chimeric antigen receptor T-cell therapy, anti-CD19 antibodies).
- 4.2.6 Clinical evidence of active CNS or testicular involvement by leukemia as documented by signs and symptoms on physical exam and/or positive LP.
 - Active CNS disease by signs and symptoms or active CNS_{2/3} disease by cell counts and cytology. History of neurologic disorder including but not limited to: prior seizure, epilepsy, structural brain abnormality, benign brain tumor, stroke, brain injuries, dementia, movement disorder or other significant CNS abnormalities.
- 4.2.7 Has a known additional malignancy that is progressing or requires active treatment. Exceptions include basal cell carcinoma of the skin, squamous cell carcinoma of the skin, or in situ cervical cancer that has undergone potentially curative therapy.
- 4.2.8 Burkitt lymphoma/leukemia
- 4.2.9 Has a diagnosis of congenital immunodeficiency
- 4.2.10 Has a known history of active TB (Bacillus Tuberculosis)
- 4.2.11 Known HIV infection
- 4.2.12 Active hepatitis B or hepatitis C infection
- 4.2.13 Any uncontrolled infection
- 4.2.14 Has received a live vaccine within 30 days prior to first dose
- 4.2.15 Is pregnant or breastfeeding, or expecting to conceive or father children within the projected duration of the trial, starting with the pre-screening or screening visit through 120 days after the last dose of trial treatment.
- 4.2.16 Non-pregnant, non-breast-feeding women may be enrolled if they are willing to use 2 methods of birth control or are considered highly unlikely to conceive. Highly unlikely to conceive is defined as 1) surgically sterilized, or 2) postmenopausal (a woman who is ≥45 years of age and has not had menses for greater than 1 year will be considered postmenopausal), or 3) not heterosexually active for the duration of the study. The two birth control methods can be either two barrier methods or a barrier

method plus a hormonal method to prevent pregnancy. Subjects should start using birth control from study Day 1 throughout the study period up to 120 days after the last dose of study therapy.

- 4.2.17** History of autoimmune disease
- 4.2.18** Known interstitial lung disease
- 4.2.19** Any evidence of active, non-infectious pneumonitis or has a history of (non-infectious) pneumonitis that required steroids or current pneumonitis
- 4.2.20** Patients who have received chemotherapy or radiotherapy within 2 weeks prior to entering the study or has not recovered from adverse events due to agents administered more than 2 weeks earlier.
- 4.2.21** Patients who are less than 4 weeks from surgery or have insufficient recovery from surgical-related trauma or wound healing.
- 4.2.22** History of allergic reactions attributed to compounds of similar chemical or biologic composition to Blinatumomab or Pembrolizumab or other agents used in study.
- 4.2.23** Known impaired cardiac function including any of the following:
 - History or presence of clinically significant ventricular or atrial tachyarrhythmias;
 - Clinically significant resting bradycardia (< 50 beats per minute);
 - Myocardial infarction within 1 year of starting study drug;
 - Other clinically significant heart disease (e.g., unstable angina, congestive heart failure, or uncontrolled hypertension).
- 4.2.24** Any condition that requires the use of corticosteroids outside of corticosteroids defined in the protocol after Day 1 of therapy with the exception of topical or inhaled steroids
- 4.2.25** Severe or uncontrolled medical disorder that would, in the investigator's opinion, impair ability to receive study treatment (i.e., uncontrolled diabetes, chronic renal disease, chronic pulmonary disease or active, uncontrolled infection, psychiatric illness/social situations that would limit compliance with study requirements.

5. TREATMENT PLAN

5.1 Treatment dosage and administration

5.1.1 Treatment summary

The study will be conducted in 2 stages:

Stage 1 is to ensure safety of pembrolizumab in combination with blinatumomab.

Dose Limiting Toxicity (DLT) is defined as a clinically significant adverse event that is considered by the investigator to be probably or definitely related to pembrolizumab or the combination of pembrolizumab and blinatumomab occurring within 42 days of the first dose of pembrolizumab on Day 15 of Cycle 1 as follows:

- Any Grade 3-5 non-hematologic toxicity EXCEPT:
 - Grade 3 cytokine release syndrome that resolves in 7 days or less
 - Grade 3 neurotoxicity that resolves in 7 days or less
 - Grade 3 infections
 - Grade 3 or 4 febrile neutropenia unless deemed by investigator to be definitely related to pembrolizumab
 - Grade 3 or 4 laboratory abnormalities unless they warrant temporary discontinuation of pembrolizumab or permanent discontinuation of blinatumomab (see tables, 5.7.1 and 5.7.2)
 - Grade 3 or 4 lymphopenia
- Any clinically significant toxicity that precludes administration of the next scheduled dose for more than 14 days

If no DLTs are experienced in the first 3 subjects then enrollment will advance Stage 2. If 1 DLT is noted in the first 3 subjects then 3 additional subjects will be enrolled. If no further DLTs are noted in the additional 3 subjects then enrollment will proceed to Stage 2. If 2 or more DLTs are noted at the proposed pembrolizumab dose level and schedule then enrollment will be placed on hold and a dose reduction or schedule change will be considered after discussion of investigators.

The DLT monitoring period will be 42 days starting on Day 15 of Cycle 1. Subjects withdrawing from investigational treatment during the DLT monitoring period for a reason that is definitely unrelated to toxicity of the study agent (e.g. disease progression, patient withdrawal of consent) will be deemed not evaluable for DLT determination and will be replaced. All subjects in Stage 1 will need to complete the DLT monitoring period prior to proceeding with Stage 2.

Stage 2 of the study will include an expansion cohort of up to 21 additional subjects (for a total of 24 subjects) to evaluate the efficacy of the combination of blinatumomab and pembrolizumab.

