5.7 Toxicities and Dosing Delays/Dose Modifications

Any patient who receives treatment on this protocol will be evaluable for toxicity. Each patient

will be assessed for the development of toxicity except cytokine release syndrome (see below, grading/management per Lee et al. Blood 2014) according to the NCI Common Toxicity Criteria for Adverse Events (CTCAE), version 4.03. Dose adjustments should be made according to the system showing the greatest degree of toxicity. As Blinatumomab is an approved treatment for this indication, reducing or withholding pembrolizumab should be considered as the first option in response to a toxicity prior to adjusting the Blinatumomab dosing.

Adverse events (both non-serious and serious) associated with pembrolizumab exposure may represent an immunologic etiology. These adverse events may occur shortly after the first dose or several months after the last dose of treatment. Pembrolizumab and blinatumomab must be withheld for drug-related toxicities and severe or life-threatening AEs as per Tables below. See Section 5.6.1 in Events of Clinical Interest Guidance Document for additional supportive care guidelines.

All dose adjustments presume that the toxicity is determined by the investigator to be possibly, probably, or definitely related to blinatumomab, pembrolizumab, or both. Withholding the dose and dose adjustments should not occur if toxicity is felt unlikely to be or definitely not related to study blinatumomab, pembrolizumab, or both.

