8.4 Relationship

Attribution categories for adverse events in relationship to protocol therapy are as follows:

Definite – The AE *is clearly related* to the study treatment.

Probable – The AE *is likely related* to the study treatment.

Possible – The AE *may be related* to the study treatment.

Unlikely – The AE *is doubtfully related* to the study treatment.

Unrelated – The AE *is clearly NOT related* to the study treatment.

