10.4 Evaluable Subjects and Subject Replacement

Stage 1 (Safety evaluation)

Evaluable subjects are defined as any patient receiving the combination of blinatumomab and pembrolizumab starting day 15 of Cycle 1. The DLT monitoring period will be 28 days starting Day 15 of Cycle 1. Subjects withdrawing from investigational treatment during the 28 day DLT monitoring period for a reason that is definitely unrelated to toxicity of the study agent (e.g. disease progression, patient withdrawal of consent) will be replaced for the safety analysis. 3-6 patients will be enrolled at in Stage 1 as determined by 3+3 rules. These patients will also be evaluated for efficacy.

Stage 2

Stage 2 of the study will include an expansion cohort of up to 21 additional subjects for a total of 24 subjects to evaluate the efficacy of the combination of blinatumomab and pembrolizumab. All patients receiving combination therapy starting day 15 of cycle 1 will be considered evaluable for overall response rate of entire population, RFS and OS.

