10.5 Data Analyses Plans

10.5.1 Primary Analysis

Simon's 2-stage for efficacy

We plan a Simon's 2-stage MiniMax design evaluation of the combination of blinatumomab and pembrolizumab in relapsed or refractory B-cell ALL with >50% blasts in the marrow.

We assessed the sample size for studying using overall response rate (CR + CRh). From recent large Phase II study including 189 subjects with relapsed/refractory B-lineage ALL, ORR (CR + CRh) to blinatumomab monotherapy was approximately 29% in patients with >50% lymphoblasts in the bone marrow (Topp et al. 2015). Response rates for PD-1 inhibitors in relapsed or refractory ALL are unknown but given mechanism of action it likely approaches zero.

An absolute increase in the overall response rate of 25 percentage points (i.e. to 54% ORR in patients evaluable for efficacy) or greater will demonstrate sufficient activity to consider the regimen for further study.

To calculate sample sizes for Stage 1 and Stage 2 we used a probability of type I error (α) = 0.05 and a power ($1-\beta$) = 0.80 with $p_0=0.29$ and $p_1=0.54$.

The null hypothesis that the true response rate is 0.29 will be tested against a one-sided alternative. In the first stage, 18 patients evaluable for efficacy will be accrued. If there are 7 or fewer responses in these 18 patients, the study will be stopped. Otherwise, 6 additional patients will be accrued for a total of 24 patients evaluable for efficacy of the combination. The null hypothesis will be rejected if 11 or more responses are observed in 24 evaluable patients. This design yields a type I error rate of 0.05 and power of 0.80 when the true response rate is 0.54. The likelihood of early termination is 0.88, if the null hypothesis is true.

Safety rules

At the time of the Stage 1 efficacy analysis, all patients will be reviewed again for DLTs as defined in Section 5.1.4 occurring at any time during therapy.

A DLT rate exceeding 0.3 will be considered unacceptable. The first 3, 6, 12, and 24 patients will be monitored for DLTs. The first 6 patients will be monitored every other week. The next 6 patients will be monitored monthly. Subsequent patients will be monitored every other month.

k	1	2	3	4
n_k	3	3	6	12

N_k	3	6	12	24
r_k	1	1	3	5

Table: Monitoring design for DLTs. The stage is denoted by k . The number of patients accrued during and up to stage k are denoted by n_k and N_k respectively. The critical value at stage k is denoted by r_k .

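### The Stage 1 replacement rule has no exception for a subject who already had a DLT, so a DLT followed by progression or withdrawal of consent drops out of the 3+3 count

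*Combined protocol and SAP*

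**What the plan says.** **Replacement.** Under Section 5.1.1, a Stage 1 subject who leaves treatment in the DLT window for a reason "definitely unrelated to toxicity of the study agent (e.g. disease progression, patient withdrawal of consent) will be deemed not evaluable for DLT determination", and is replaced. Section 5.1.4 repeats the replacement on the same ground. Section 10.4 does so too, and says such subjects "will be replaced for the safety analysis".

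**What counts as a DLT.** The event must be "considered by the investigator to be probably or definitely related to pembrolizumab or the combination of pembrolizumab and blinatumomab" (5.1.1, repeated in 5.1.4). Section 8.4 has categories below that threshold. For Possible, the wording is "The AE *may be related* to the study treatment". Dose adjustments start from the lower level: "All dose adjustments presume that the toxicity is determined by the investigator to be possibly, probably, or definitely related to blinatumomab, pembrolizumab, or both" (5.7).

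**Who is evaluable.** Section 10.4 says: "Evaluable subjects are defined as any patient receiving the combination of blinatumomab and pembrolizumab starting day 15 of Cycle 1". It sets no minimum follow-up. Section 5.1.1, directly after the replacement rule, requires all Stage 1 subjects to complete the monitoring period before Stage 2 opens.

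**Window.** Section 5.1.1 says: "The DLT monitoring period will be 42 days starting on Day 15 of Cycle 1". Section 10.4 gives 28 days from the same start.

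**Decision rule and later looks.** Under 5.1.4, no DLT in three subjects means proceed, one in three means add three more, at most one in six means proceed, and two or more means hold. Section 10.5.1 treats a DLT rate above 0.3 as unacceptable and sets looks at 3, 6, 12 and 24 patients. Its table note describes the counts with the words "The number of patients accrued during and up to stage" k. It also has DLTs in all patients reviewed again at the Stage 1 efficacy analysis, which needs 18 evaluable patients.

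**The concern.** Whether a subject informs the DLT decision should depend on two facts: whether a DLT occurred, and if not, whether the window was completed. The replacement rule uses a third fact, the reason for leaving. A subject can have a DLT and later leave for a reason that has nothing to do with toxicity. The rule then removes an event that was actually observed.

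The sequence is plausible under this schedule. Section 5.1.3 takes a subject who progresses after Cycle 1 Day 15 off study. The Cycle 1 marrow on Day 29 + 8 days (Days 29 to 37) falls inside the window on either stated length: 28 days from Day 15 runs through Day 42, and 42 days runs through Cycle 2 Day 14.

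At stake is the go/no-go decision for a new combination, made on three to six people, where one event can change the outcome. Adverse event reporting is not at stake: Sections 5.7, 7.1.1 and 7.2 keep treated patients in the toxicity data.

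**Working it through.** The documents state no operating characteristics for the run-in, so there is no plan figure to reproduce. The figures below come from the decision rule in 5.1.4, with subjects treated as independent and p as the true DLT rate. The values of p are illustrations: 0.30 is the limit in 10.5.1, and 0.40 lies above it.

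**Step 1. Run-in as designed.**
P(proceed) = (1−p)³ + 3p(1−p)²·(1−p)³.
- p = 0.30: 0.343 + 0.151 = 0.494.
- p = 0.40: 0.309.

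**Step 2. One DLT in the first three, and that subject then leaves for progression.** The other two are taken as DLT-free completers, and the replacement as evaluable.
- DLT counts: three more subjects must all be DLT-free, so P = (1−p)³.
- Subject replaced: either the replacement is DLT-free (0 of 3, proceed), or the replacement has a DLT and three further subjects are clean. P = (1−p) + p(1−p)³.

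| p | DLT counts | Subject replaced |
|---|---|---|
| 0.30 | 0.7³ = 0.343 | 0.7 + 0.3 × 0.343 = 0.803 |
| 0.40 | 0.6³ = 0.216 | 0.6 + 0.4 × 0.216 = 0.686 |

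This step needs no assumption about how often subjects leave.

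**Step 3. Two DLTs in the first three, one of them erased.** If both count, the study is held and the chance of proceeding is 0. If one subject is replaced, the replacement and three further subjects must all be clean: 0.7 × 0.343 = 0.240 at p = 0.30, and 0.6 × 0.216 = 0.130 at p = 0.40.

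**Step 4. Average effect.** Let a and b be the probabilities of leaving for a definitely unrelated reason with and without a DLT. The documents give neither, so both are assumptions. Replaced subjects leave numerator and denominator, so the recorded rate is p(1−a) / [p(1−a) + (1−p)(1−b)]. At p = 0.30 and b = 0.2:

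| a | Recorded rate | P(proceed) |
|---|---|---|
| 0.2 | 0.24/0.80 = 0.300 | 0.494 |
| 0.4 | 0.18/0.74 = 0.243 | 0.614 |
| 0.6 | 0.12/0.68 = 0.176 | 0.759 |

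With a = b the recorded rate equals the true rate. It falls only when a exceeds b.

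**Step 5. Early leavers without a DLT.** Replacement needs a reason definitely unrelated to toxicity, and a DLT needs probable or definite attribution. A subject who stops early for toxicity rated possible meets neither test. Section 10.4 makes that subject evaluable. The completion sentence in 5.1.1 points the other way, but does not say that a non-completer is unevaluable or replaced, and it is absent from 5.1.4 and 10.4. Under Section 8.1, adverse event monitoring can end 30 days after the last dose. A subject who stops both drugs in the first 12 days of a 42-day window (42 − 30 = 12) need not be observed to its end.

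On the 10.4 reading, if a share u of subjects leave this way and a share m of their DLT risk goes unseen (both assumed), the recorded rate is p(1−u·m). At p = 0.30, u = 0.1 with m = 0.5 gives 0.285 and P(proceed) 0.525. With u = 0.33 and m = 0.75 the figures are 0.226 and 0.653.

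**The case against.** **The rule need not un-count a DLT.** Only 5.1.1 uses the not-evaluable wording. Section 5.1.4, which holds the stopping rules, says only that the subject is replaced, and a hold is triggered by DLTs that are noted. A sensible team would keep the event. That is a fair reading of 5.1.4 alone, but 5.1.1 goes further and makes the subject unusable for DLT determination. The sections should not need goodwill to agree.

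**There is a backstop.** Section 10.5.1 reviews DLTs in all patients again. This stands, but the review comes at the efficacy look, after the run-in decision.

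**A reader might infer that the rule always lowers the observed DLT rate.** It does not: Step 4 shows no average bias when leaving is unrelated to having a DLT.

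**A reader might also infer that the plan plainly counts unfinished subjects as DLT-free.** The completion sentence in 5.1.1 tells against that. The DLT item on toxicity delaying the next dose by more than 14 days also catches some early stops when attribution is probable or definite. What remains is a conflict between 5.1.1 and 10.4.

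**Finally, a reader might infer that early leavers pad the looks at 12 and 24 patients.** That rests on the word accrued in a table note. The operative text speaks of the first 3, 6, 12 and 24 patients monitored for DLTs, and no withdrawal rates are given, so the documents support no figure for it.

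**Conclusion.** The concern holds for the erased DLT. Three sections key replacement to the reason for leaving, one makes the subject unusable for the DLT decision, and none exempts a DLT already seen. When it happens, one erased event moves the chance of proceeding from 0.343 to 0.803 at a true rate of 0.30, and from 0.216 to 0.686 at 0.40. These figures are conditional on one DLT in the first three followed by such a departure. How often that would occur cannot be derived from the documents, and a downward bias on average requires subjects with a DLT to leave more often than others.

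The treatment of early leavers without a DLT is a secondary point: an ambiguity between 10.4 and 5.1.1, with a size that depends wholly on assumed departure rates. The accrued wording in 10.5.1 needs clarifying, no more. This should be fixed, but it does not invalidate the design.

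**What to change.** 1. In 5.1.1, 5.1.4 and 10.4, state that any DLT in the monitoring period counts and that the subject is not replaced, whatever the later reason for leaving.
2. Reconcile the evaluable definition in 10.4 with the completion sentence in 5.1.1, so that a subject without a DLT counts as DLT-free only after completing the period. Whether a subject withdrawn for possibly related toxicity is then replaced is open to debate. The protocol should state its choice, but this point does not require replacement.
3. Reconcile the 42-day window in 5.1.1 with the 28-day window in 10.4. A definition based on completion cannot work while both stand.
4. In 10.5.1, state that the denominators at the DLT looks are DLT-evaluable patients who received the combination, and report the number not evaluable at each look.

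**Cost.** Protocol wording, and possibly a slightly later run-in decision. The rule also becomes deliberately cautious: every DLT is kept while some DLT-free leavers are replaced. At p = 0.30 with b = 0.2 the recorded rate is 0.30/(0.30 + 0.70 × 0.8) = 0.349, and the chance of proceeding is 0.399 instead of 0.494. In a run-in meant to establish safety, that is an acceptable direction of error, since a hold leads to discussion and not to automatic closure.

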5.1.2 Other therapeutic agents

The use of therapeutic agents or approaches for malignancy outside of what is expressly stated in this protocol is strictly forbidden. This includes any study undefined use of the study specific therapeutic agents, the same class of agents, or agents not expressly defined in the protocol

with potential or known anti-leukemic activity. Institutional standard of care supportive medications are allowed as long as they do not have known or predicted anti-leukemic activity or are in conflict with study dictated supportive care.

5.1.3 Therapy

[figure not shown]
Both Stage 1 (safety lead-in) and Stage 2 (dose expansion) of this study will use the same regimen as detailed below.

Schema:

Cycle 1

Cycle 2-5

REGIMEN DESCRIPTION					
CYCLE 1					
Agent	Premedications; Precautions	Dose	Route	Schedule	Cycle Length
Blinatumomab	Dexamethasone 20 mg IV once 1 hour (+/- 30 min) before start of infusion and 1 hour (+/- 30 min) prior to step-up dose on Day 8.	Day 1-7: 9 mcg/day	Continuous IV infusion for 28 days. Bag changes every, 24 hours, 48 hours or 7 days (as appropriate).	Day 1-7	6 weeks (42 days)
		Day 8-28: 28 mcg/day		Day 8-28	
Pembrolizumab	None required, per institutional	200 mg	IV over 30 minutes	Days 15 and 36	

	standard of care				
Methotrexate	None required, per institutional standard of care	15 mg	Intrathecal or intraventricular	Day 29 + 8 days	
CYCLES 2-5					
Blinatumomab	Dexamethasone 20 mg IV once 1 hour (+/- 30 min) before start of infusion.	28 mcg/day	Continuous IV infusion for 28 days. Bag changes every 24hours, 48 hours or 7 days (as appropriate).	Days 1-28	6 weeks (42 days)
Pembrolizumab	None required, per institutional standard of care	200 mg	IV over 30 minutes	Days 15 and 36	
Methotrexate	None required, per institutional standard of care	15 mg	Intrathecal or intraventricular	Day 29 + 8 days	

See **Section 9.1** for details on administration of blinatumomab

Hospitalization requirements:

Cycle 1:

Hospital admission required from day 1 through day 18 and for at least 72 hours after pembrolizumab dose.

Cycle 2:

Hospital admission required day 1-3 for blinatumomab and for at least 72 hours after start of blinatumomab infusion.

Cycles 3-5:

Hospital admission required day 1-3 for blinatumomab and for at least 72 hours after start of blinatumomab infusion.

Hospital admission also required for any blinatumomab restart or step-dose increase and for 72 hours after restart or step-up dose.

Vital signs (heart rate and oxygen saturation) to be monitored continuously and full vital signs (temperature, heart rate, blood pressure, respiratory rate, and oxygen saturation) every 4 hours

during at least the initial 72 hours of blinatumomab therapy, for 72 hours after all restart or step-up doses, and for at least the initial 72 hours following the first (Cycle 1, Day 15) pembrolizumab doses.

CNS Prophylaxis:

Methotrexate 15mg intrathecal or intraventricular at screening, day 29 + 8 days of cycle 1-4, and day 38 +8 days of cycle 5 (end of treatment)

Patients achieving a CR/CRh after 2 cycles will complete a total of 5 cycles of blinatumomab and pembrolizumab in the absence of relapse.

Patients not achieving a CR/CRh after 2 cycles of therapy or progressing after Day 15 of Cycle 1 will go off study.

Patients may proceed to allogeneic hematopoietic cell transplantation as consolidation any time after complete remission. Such patients will be censored for survival at time of initiation of conditioning regimen.

